5.1 Sample Size

Approximately 650 subjects are planned to be randomized in this study. To test the secondary endpoint of IGA success in subjects with a vIGA-AD score of ‘Moderate’ at randomization, approximately 490 of the subjects to be accrued will have vIGA-AD score of ‘Moderate’ at randomization. Randomization will be stratified by vIGA-AD score (‘Mild’ vs. ‘Moderate’), and study site.

This study is designed to differentiate between a vehicle cream treatment that has an IGA success rate of 22% or less and ARQ-151 cream treatment with an IGA success rate of 37% or more. The hypothesis is that the IGA success rate among subjects treated with ARQ-151 cream 0.05% is significantly greater than the IGA success rate among subjects treated with vehicle cream.

This sample size provides more than 90% power to detect 15% difference between treatment groups on vIGA-AD success at Week 4 at $\alpha=0.025$ using a 2-sided stratified Cochran-Mantel-Haenszel (CMH) test. The results from a recent phase 2 study (ARQ-151-212) of ARQ-151 cream 0.05% compared to vehicle treatment were used to estimate the treatment difference. The vIGA-AD success rate at Week 4 was approximately 38% in the ARQ-151 cream 0.05% group compared to 22% in the vehicle. Similarly, approximately 37% of subjects demonstrated vIGA-AD success at Week 4 in the ARQ-151 cream 0.15% group. This sample size also provides more than 80% power to detect an overall 15% difference between treatment groups on IGA success at Week 4 in subjects with vIGA-AD score ‘moderate’ at randomization. The same testing method, the stratified CMH test, will be used as for the primary endpoint.

 Innovaderm Research	STATISTICAL ANALYSIS PLAN, Version 1.0
Protocol Number: ARQ-151-315	Sponsor: Arcutis Biotherapeutics, Inc.

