6 STATISTICAL CONSIDERATIONS

6.1 Adjustments for Covariates

The covariate for this study is baseline vIGA-AD (vIGA-AD=2 - Mild vs. vIGA-AD=3 - Moderate at randomization). The CMH test will not be stratified by study site as the 650 subjects will be randomized by over 90 sites leading to a low subject to site ratio. Subgroup analyses will be generated for the baseline covariates.

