8 DEMOGRAPHIC AND OTHER BASELINE CHARACTERISTICS

Demographics and baseline characteristics will be summarized with descriptive statistics using the ITT and safety population. The list of demographics and baseline characteristics to be summarized will include:

- Age (years)
- Sex at birth
- Ethnicity
- Race*
- Baseline Height (cm)
- Baseline Weight (kg)
- Baseline Body Mass Index (BMI) percentile
- Fitzpatrick Skin Type
- Prior failure of Topical Corticosteroids, Topical Calcineurin Inhibitors, Eucrisa
- Atopic Dermatitis involvement on the face, on the eyelids

 Innovaderm Research ■■■	STATISTICAL ANALYSIS PLAN, Version 1.0
Protocol Number: ARQ-151-315	Sponsor: Arcutis Biotherapeutics, Inc.

- Number of AD flares in the last 12 months
- Number of prior prescription treatments ever used
- Duration of disease (months)
- Baseline vIGA-AD
- Average weekly baseline WI-NRS
- Daily baseline WI-NRS
- Baseline BSA (%)
- Baseline BSA (%) Group - <10% and ≥10%, tertile groups
- Baseline EASI total score
- Baseline EASI score group - ≤7 and >7, tertile groups
- Baseline SCORAD
- Baseline CDLQI (≥ 4 years of age)
- Baseline IDQoL (< 4 years of age)
- Baseline DFI
- Baseline POEM

*Subjects who reported more than one race will be summarized as 'Multiple' races in the table. All races selected will be displayed in the listing.

BMI (kg/m²) = (weight in kg)/ [(height in cm/100)²]. Baseline height will be used to derive BMI for all post-baseline visits until height is collected again (planned at week 4). After BMI is calculated using the same formula above for children, it is expressed as a percentile obtained from either a graph or a percentile calculator. Percentiles will be calculated using data files and instructions provided by the CDC (https://www.cdc.gov/growthcharts/percentile_data_files.htm).

A listing of all demographics, analysis population flag, reason not included in the efficacy analysis will be provided.

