12.1.3 Primary Endpoint Analysis

For the primary analysis, missing vIGA-AD scores will be imputed using multiple imputation as described in Section 6.2.1. These imputations will result in a minimum of 25 to a maximum of 250 complete analysis datasets, depending on the number of imputed monotone datasets that are required.

Percentages of subjects having a vIGA-AD Success (refer to Section 12.1.1) will be presented by visit and treatment group based on multiply imputed data in the ITT population along with both 97.5% and 95% Wilson CIs. The common MH odds ratio and common MH proportion difference, adjusted for the randomization factor (i.e., randomized vIGA-AD score) will also be provided along with their common associated 97.5% and 95% CIs. Additionally, count and percentage of subjects having a vIGA-AD success, count and percentage of subjects in each category of the vIGA-AD scale, and descriptive statistics for the vIGA-AD scores, change in vIGA-AD score from baseline and percent change in vIGA-AD score from baseline will be presented by visit and treatment group based on observed data in the ITT population.

The primary endpoint (vIGA-AD Success at Week 4) will then be analyzed using multiple imputation CMH test stratified by randomized baseline vIGA-AD. To do so, a CMH analysis will be performed separately for each of the complete multiply imputed analysis data sets, and results will be combined into one multiple imputation inference using the methodology described in Section 6.2.1. Statistical significance will be concluded at the 2.5% significance level (2-sided). Should the odds ratio be not estimable for at least one multiply imputed dataset, the conclusion of

 Innovaderm Research ■■■	STATISTICAL ANALYSIS PLAN, Version 1.0
Protocol Number: ARQ-151-315	Sponsor: Arcutis Biotherapeutics, Inc.

the study will be based on the p-value obtained from a MH test, stratified by randomized baseline vIGA-AD, for the common MH proportion difference at Week 4.

The following sensitivity and supplemental analyses to the primary analysis of the primary endpoint will be performed:

- Tipping Point analysis (refer to Section [6.2.3](#)) on ITT population.
- Non-responder imputation (refer to Section [6.2.2](#)) on ITT population.
- Observed data on ITT population (refer to Section [4.1](#)).
- Observed data on PP population (refer to Section [4.2](#)).

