12.2 Secondary Efficacy Endpoints Analysis

Secondary efficacy endpoints are based on the vIGA-AD scale or EASI questionnaire. The list of secondary efficacy endpoints can be found in Section [2](#) and their derivation in Section [5.5](#).

- For more details about the vIGA-AD scale refers to Section [12.1.1](#).
- For the EASI questionnaire, four anatomic sites (head, upper extremities, trunk, and lower extremities) are assessed for erythema, induration/infiltration (papules), excoriation, and

 Innovaderm Research	STATISTICAL ANALYSIS PLAN, Version 1.0
Protocol Number: ARQ-151-315	Sponsor: Arcutis Biotherapeutics, Inc.

lichenification as seen on the day of the examination. The severity of each sign is assessed using a 4-point scale (half steps are allowed e.g., 0.5): 0 (none), 1 (mild), 2 (moderate), and 3 (severe). The area affected by AD within a given anatomic site is estimated as a percentage of the total area of that anatomic site and assigned a numerical value according to the degree of AD involvement as follows: 0 (no involvement), 1 (1-9%), 2 (10-29%), 3 (30-49%), 4 (50-69%), 5 (70-89%), and 6 (90-100%).

For each secondary efficacy endpoint, missing data will be imputed and data will be summarized as for the primary efficacy endpoint (refer to Section 12.1.3).

Upon successful demonstration of statistical significance for the primary efficacy endpoint, the secondary efficacy endpoints will be tested sequentially at an alpha level of 0.025.

The secondary efficacy endpoint of vIGA-AD success among subjects with vIGA-AD score of ‘Moderate’ at randomization will be analyzed as described for the primary efficacy endpoint (refer to Section 12.1.3) but based on the vIGA-AD Moderate ITT population (refer to Section 4.3) and use of a chi-square test to evaluate the treatment effect. That is, as per the vIGA-AD Moderate ITT population definition all subjects included in this analysis will have a randomized vIGA-AD score of Moderate (3) and so, the CMH test cannot be used.

The remaining secondary efficacy endpoints, comprised of the endpoints of EASI-75 at Week 4, vIGA-AD of ‘clear’ or ‘almost clear’ at Week 4, vIGA-AD of success at Week 2, vIGA-AD of ‘clear’ or ‘almost clear’ at Week 2, vIGA-AD of success at Week 1 and vIGA-AD of ‘clear’ or ‘almost clear’ at Week 1 will be performed as described for the primary efficacy endpoint (refer to Section 12.1.3) based on the ITT population (refer to Section 4.1).

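### Valid responder tests leave baseline EASI unused; stratifying by it, above all in the gating Moderate-subset test, could add a little power at almost no cost

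*SAP*

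**What the plan says.** SAP 6.1 names a single covariate: "The covariate for this study is baseline vIGA-AD", at two levels, Mild and Moderate. Site was a randomization factor but is left out of the analysis because there are few children per site. SAP 12.1.3 and 12.2 apply this CMH test to the primary endpoint and to every secondary endpoint except one.

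The exception is vIGA-AD success at Week 4 in children randomized as Moderate. SAP 6.2.1, 12.2 and Table 5, and Protocol 8.2.1, give it an unstratified chi-square test. SAP 12.2 argues that all these children share one randomized score, so "the CMH test cannot be used". SAP 5.1 and Protocol 8.1.1 say instead that this endpoint uses the same stratified CMH test as the primary. Protocol 8.2.1 lists it first among the secondary endpoints, and under SAP 6.5 a p-value above 0.025 there ends formal testing of the six that follow.

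Baseline EASI of at least 5 is an inclusion criterion (Protocol 6.6.1). SAP 8 lists "Baseline EASI score group" with a cut at 7, and SAP 6.6 uses the same cut for subgroups. The continuous exploratory endpoints are adjusted for their own baseline (SAP 12.3). The responder endpoints, EASI-75 included, are not.

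**The concern.** If baseline EASI predicts success among children of the same vIGA-AD grade, a test that ignores it carries avoidable variance. Most of any gain would fall on the Moderate-subset test. It has the smaller sample, the lower stated power (more than 80%, against more than 90% for the primary) and no adjustment at all, and it controls access to six further endpoints. The value is already collected and the cut already defined, so no data-driven choice would be needed.

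**Working it through.** **Inputs from the documents.** SAP 5.1 plans for success in 22% of children on vehicle and 37% on active cream, with 650 children in all and about 490 Moderate. Allocation is 2:1, which gives 433:217 overall (protocol synopsis) and about 327:163 for Moderate. Alpha is 0.025 two-sided, so z = 2.2414. The sample size section states no dropout allowance, and none is used here.

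**Assumed, because the documents are silent.** (a) The odds ratio for success between children at or below EASI 7 and those above it, within vIGA-AD grade: 1 to 4. (b) The share above 7: 40% to 85%.

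**Step 1: the plan's own figures.** Power = Φ[(d − z·SE0)/SE1], with SE0 from the pooled rate and SE1 from the two separate rates.

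Moderate subset:
- pooled rate = (327×0.37 + 163×0.22)/490 = 0.3201
- SE0 = √[0.3201×0.6799×(1/327 + 1/163)] = 0.04473
- SE1 = √[0.37×0.63/327 + 0.22×0.78/163] = 0.04202
- power = Φ[(0.15 − 2.2414×0.04473)/0.04202] = Φ(1.184) = 88.2%

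The same formula with 433:217 gives SE0 = 0.03880, SE1 = 0.03646 and power 95.8%. Both stated figures (more than 80% and more than 90%) are reproduced.

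**Step 2: adding the EASI stratum.** The arm averages stay at 37% and 22%, and each arm is split into EASI groups with the assumed odds ratio. Worked case, odds ratio 3 with 60% above 7:
- active: 26.78% above 7 and 52.32% at or below (0.6×26.78 + 0.4×52.32 = 37.0)
- vehicle: 14.36% and 33.46% (0.6×14.36 + 0.4×33.46 = 22.0)
- MH difference = 0.6×12.42 + 0.4×18.86 = 15.0 points, unchanged
- pooled rates by group are 0.2265 and 0.4605, so SE0 = √[(0.6×0.2265×0.7735 + 0.4×0.4605×0.5395)×(1/327 + 1/163)] = 0.04336
- SE1, weighted by stratum in the same way, = 0.04079
- power = Φ[(0.15 − 2.2414×0.04336)/0.04079] = Φ(1.295) = 90.2%

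Moderate-subset power with EASI strata (planned test: 88.2%):

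| Assumed odds ratio | 40% above 7 | 60% above 7 | 85% above 7 |
|---|---|---|---|
| 1 | 88.2% | 88.2% | 88.2% |
| 1.5 | 88.4% | 88.5% | 88.3% |
| 2 | 88.9% | 89.0% | 88.7% |
| 3 | 89.9% | 90.2% | 89.5% |
| 4 | 90.8% | 91.3% | 90.2% |

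For the primary endpoint at 60% above 7, taking the same rates in both vIGA-AD grades, power goes from 95.8% to 96.0%, 96.2%, 96.8% and 97.3% at odds ratios 1.5, 2, 3 and 4. There is less room to gain.

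**Step 3: simulation check.** Simulated Moderate-subset trials (40,000 per setting, 60% above 7) gave gains of about 0.3, 0.8, 2 and 3 points at odds ratios 1.5, 2, 3 and 4, in line with the table, and type I error near 2.5%. At odds ratio 1 power was 88.2% for both tests. A longer run of 200,000 trials gave 88.4% for the chi-square and 88.2% for the stratified test, so any cost is at most about 0.2 of a point.

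**Step 4: effect on the odds ratio.** Without EASI the planning odds ratio is (0.37/0.63)/(0.22/0.78) = 2.08. In the worked case it is (0.2678/0.7322)/(0.1436/0.8564) = 2.18 within each EASI group. The common odds ratio shifts slightly because it is conditional on more. The proportion difference does not shift.

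**The case against.** The strongest reply is that nothing here is wrong. Both endpoints exceed their stated power. The plan adjusts for the randomization factor it kept and explains dropping site. In the Moderate subset that factor is constant, so a chi-square follows. This stands, and it rules out a reading that the missing adjustment makes the tests invalid or underpowered.

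The gain also rests on a quantity the documents do not give, and they offer some reason to expect it to be modest. Entry requires EASI of at least 5, so the lower group covers only 5 to 7. vIGA-AD already captures much of severity. EASI mainly adds extent, which vIGA-AD uses only for indeterminate cases, and excoriation, which vIGA-AD excludes. Whether these predict success within grade is unknown. This stands too.

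The change reaches beyond the SAP. The protocol names the tests, SAP 3.5 declares no departures from it, and the primary estimand is summarized by an odds ratio whose conditioning would change. Mild children number about 650 − 490 = 160, roughly 53 on vehicle, and a Mild child succeeds only by reaching clear, so splitting that grade may leave thin strata. These points shape the fix but do not defeat it.

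The reply does not remove the asymmetry: at most about 0.2 of a point lost, up to about 3 gained, on the test that opens the rest of the sequence. Nor does the statement that "the CMH test cannot be used" settle the matter, since it holds only while vIGA-AD is the sole stratum.

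**Conclusion.** This is an optional improvement. The planned tests are sound, but they leave unused a baseline value that the trial already collects and groups. At the planning rates, Moderate-subset power changes from about 88.2% by 0 to +3 points over odds ratios of 1 to 4 and 40% to 85% of children above EASI 7. The primary endpoint gains at most about 1.5 points at 60% above 7. Type I error stays near 2.5%. The calculations assume complete data and a constant odds ratio across EASI groups.

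A reader might infer that a material gain is assured. The documents do not support that: below an odds ratio of 2 the gain is under one point, and a lopsided split shrinks it further. A reader might also expect gains near 6 points. That size arises only with a logistic model on continuous EASI and an odds ratio of 3 per standard deviation, which is a different analysis resting on a strength the documents do not establish. No size is given for EASI-75, because the documents state no planning rates for it.

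**What to change.** Before unblinding:

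- In SAP 6.1 and 12.2, add baseline EASI group (at or below 7, above 7) as a CMH stratum, at least for the Moderate-subset test and EASI-75. Preferably extend it to all ITT responder endpoints (also SAP 12.1.3), giving four strata. For the Moderate subset a two-stratum CMH replaces the chi-square. SAP 6.2.1, 12.2, Table 5 and Protocol 8.2.1 can then be brought into line with SAP 5.1 and Protocol 8.1.1, a conflict that needs reconciling in any case.
- State a numeric collapsing rule on pooled counts, so that it can be applied blind. For example, drop the EASI split within a vIGA-AD grade if either group has fewer than 30 children. Under 2:1 allocation that means about 30/3 = 10 on vehicle; 10 is also the size below which SAP 12.4 makes no subgroup inference, although there it counts both arms together.
- Add baseline EASI to the vIGA-AD imputation model in SAP 6.2.1, so that imputation and analysis use the same variables. The model for other scales already includes baseline vIGA-AD.
- Record the change in SAP 3.5 and in the protocol's analysis text.
- State that the common odds ratio is conditional on vIGA-AD and EASI group. The MH proportion difference, already the supportive summary, keeps its meaning.

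The cost is document wording, one more stratification variable in the programs, and a slightly changed conditioning of the odds ratio. No new data are needed. If the sponsor prefers to leave the primary test alone, the change to the Moderate-subset and EASI-75 tests can stand by itself.

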6.2 Handling of Dropouts or Missing data

See [Appendix 2](#) for handling of completely or partially missing dates for prior and concomitant medications and AEs.

 Innovaderm Research	STATISTICAL ANALYSIS PLAN, Version 1.0
Protocol Number: ARQ-151-315	Sponsor: Arcutis Biotherapeutics, Inc.

Unless otherwise specified, missing safety data will not be imputed.

6.2.1 Multiple Imputation

All subjects, regardless of completion status, will have available data assigned to the pre-specified analysis visit using the analysis windows defined in Section 5.4, including the last available data of subjects who prematurely withdraws from the study. To comply with the definition of the primary estimand (Section 12.1.1), for subjects who discontinue due to lack of efficacy or adverse event, efficacy data assigned to a pre-specified analysis visit will be removed from the source data used for the multiple imputation process if subject's last dose day falls within the analysis visit window or is prior to the start of the analysis visit window used to assign data to a pre-specified analysis visit. This procedure will ensure that the data collected on or after these specific intercurrent events are not used in the imputation process.

For the primary efficacy endpoint of vIGA-AD success at Week 4 and the secondary endpoint of vIGA-AD success at Week 4 among subjects with a 'Moderate' randomized vIGA-AD score, the primary analysis will impute missing values using a Predictive Mean Matching (PMM) sequential-regression multiple imputation model for the ITT population. This is a three-step process.

1. The first step is to understand the pattern of missingness. In order to perform the multiple imputation, a monotone missing pattern has to be achieved. For example, if there exist values for baseline and Week 4 visits, but missing values for the Week 1 or 2 visits, the Markov-Chain Monte-Carlo (MCMC) method will be used to impute the small amount of missing data that may be missing at the intermediate visits that is required to make the missing data pattern monotone before applying the multiple imputation algorithm. This method uses a non-informative Jeffreys prior to derive the posterior mode from the expectation-maximization (EM) algorithm as the starting values for the MCMC method. The MCMC method will use the seed 6457149. The vIGA-AD score will be treated as a continuous variable for this step and the model will include the vIGA-AD scores at baseline, Week 1, Week 2, and Week 4. To avoid values that could not be observed in practice, imputed values will be rounded to the nearest integer (Round=1 option in PROC MI) in the range of 0 to 4.

To determine the number of multiply-imputed datasets to be created at this step, the proportion of datapoints with non-monotone pattern across all visits and subjects will first be derived as follows:

$$\frac{\text{number of non monotone visits accross all visits and subjects}}{\text{total number of expected visits accross all subjects}} * 100$$

 Innovaderm Research ■■■	STATISTICAL ANALYSIS PLAN, Version 1.0
Protocol Number: ARQ-151-315	Sponsor: Arcutis Biotherapeutics, Inc.

Then, the following table will be used:

Non-monotone Missing Data	Number of Imputed Datasets
$\leq 2\%$	1
$> 2\% \text{ to } \leq 5\%$	3
$> 5\%$	10

2. Once the monotone pattern is achieved, the next step is to implement the imputation algorithm. For this, the PMM regression method will be used. This method is particularly helpful if the normality assumption is violated. For subjects with complete data up to a particular visit, a PMM regression model will be fit that includes the outcome at that visit as the dependent variable and as independent variables, the treatment group, and vIGA-AD score outcomes at previous visits, using a seed of 482371. For other scales/questionnaires, the actual baseline vIGA score will also be included as an independent variable. This process will be repeated 25 times, resulting in a total of 25 to 250 complete analysis datasets, depending on the number of imputed monotone datasets that are required. The seed may be changed after unblinding in case of any issues with the imputation process, and it will be documented in the CSR if any change is required.
3. For each of the 25 to 250 completed datasets, the necessary derived variable will be computed as defined in Section 5.5 and analyzed using a CMH analysis, adjusted for the randomized vIGA-AD score for the primary efficacy endpoint. The treatment effect on the secondary efficacy endpoint dealing with vIGA-AD success in the vIGA-AD moderate ITT population will be assessed with an unstratified chi-square test. Results will be combined into one multiple imputation inference as follows:
 - a. Common proportion of success, common Mantel-Haenszel (MH) proportion difference (and associated 97.5% and 95% CIs), and common MH odds ratio (and associated common 97.5% and 95% CIs) will be combined using PROC MIANALYZE based on Rubin's rule. Common MH odds ratios and associated common 95% CI will first be normalized using a log-transformation before being combined using PROC MIANALYZE. The resulting combined common MH odds ratio and associated combined common 97.5% and 95% CIs will be back-transformed to the arithmetic scale before being presented in a table.
 - b. For the combined common proportion of success, the associated combined common 95% CI will be calculated as per Lott and Reiter multiple imputation

 Innovaderm Research ■■■	STATISTICAL ANALYSIS PLAN, Version 1.0
Protocol Number: ARQ-151-315	Sponsor: Arcutis Biotherapeutics, Inc.

Wilson interval method¹.

c. Two p-values will be produced for each analysis:

- i. The primary p-value will be obtained from a multiple imputation CMH test, where CMH general association statistics and their standard errors obtained from the analysis of each multiply-imputed dataset will be transformed as per Wilson-Hilferty² before being combined using PROC MIANALYZE based on Rubin's rule. Because the Wilson-Hilferty transformation is a monotone transformation, the p-value for the CMH test is the one-sided p-value from the t distribution. This p-value will be the primary p-value used to evaluate the result according to the multiple testing strategy described in Section 6.5.
- ii. Should the common MH odds ratio from the analysis of at least one of the multiply-imputed datasets be not estimable, combined common MH odds ratio and associated combined common CIs and p-value will not be presented. Under such circumstance, conclusions will be based on the p-value obtained from a multiple imputation test of the proportion difference, where the common proportion difference using MH weights and associated common standard errors based on the Sato variance estimator obtained from the analysis of each multiply-imputed dataset will be combined using PROC MIANALYZE based on Rubin's rule.

Similar multiple imputation method will be used for the EASI total score (refer to Section 5.5) where the missing EASI total score data at Weeks 1, 2, and 4 will be imputed, not the missing EASI question score data. Since the missing EASI total scores have a precision of 1 decimal place, the MCMC imputation for the non-monotone missing data will be restricted to values between 0 and 72, rounded to the 1st decimal (i.e., 0.1). Imputation of missing data for EASI total score will be based on the ITT population.

Even though it is only considered an exploratory endpoint, the multiple imputation methods will also be applied to the weekly average WI-NRS score at Weeks 1, 2, 3, and 4. The MCMC imputation for the non-monotone missing data will be restricted to values between 0 and 10, rounded to the 1st decimal (i.e., 0.1). Imputation of missing data for average weekly WI-NRS score will include all subjects in the ITT population.

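### Minor: SAP 6.2.1 step 1 fills Week 1 and Week 2 gaps from a model that does not list treatment, and reuses too few fills; the bias is small and the fix is cheap

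*SAP*

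**What the plan says.** SAP 6.2.1 handles missing vIGA-AD scores in three steps.

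- **Step 1** makes the missing pattern monotone. MCMC is used to "impute the small amount of missing data that may be missing at the intermediate visits", and "the model will include the vIGA-AD scores at baseline, Week 1, Week 2, and Week 4". Filled values are rounded to whole scores from 0 to 4. The number of datasets made here is 1, 3 or 10, according to whether non-monotone data are at most 2%, above 2% to 5%, or above 5%. The denominator of that percentage is the "total number of expected visits accross all subjects".
- **Step 2** imputes the remaining monotone gaps by predictive mean matching (PMM), with "as independent variables, the treatment group, and vIGA-AD score outcomes at previous visits". On repetition: "This process will be repeated 25 times, resulting in a total of 25 to 250 complete analysis datasets".
- **Step 3** analyses each dataset. The estimates "will be combined using PROC MIANALYZE based on" Rubin's rule, as are the transformed CMH statistics behind the primary p-value. No rule for nested imputation is given.

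SAP 12.2 applies this imputation to every secondary endpoint. SAP 6.5 tests them in fixed order at 0.025. The last four are vIGA-AD success and clear/almost clear at Week 2, then the same two at Week 1.

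**The concern.** Two features of step 1 depart from usual practice.

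**Treatment is not listed.** An imputation model that omits treatment gives both arms the same regression. For a missing Week 1 score, the filled arm difference is only what baseline, Week 2 and Week 4 carry. If the drug acts early, the difference is diluted. If it acts late, Week 4 pulls the filled values apart and the difference is slightly overstated. The last four endpoints are reached only after the primary and three other endpoints succeed, so the overstating direction matters for error control.

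**Step 1 fills are reused.** A value filled in step 1 is identical in all 25 PMM runs of its dataset. Ordinary pooling treats the 25, 75 or 250 results as independent imputations, so it misses some or all of the uncertainty from step 1.

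At stake is the accuracy of four alpha-controlled comparisons. Week 4 is the last visit, so step 1 never fills a Week 4 value. The primary and other Week 4 endpoints are touched only indirectly, where filled Week 1 or 2 scores serve as predictors in step 2.

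**Working it through.** **Inputs from the documents.** 433 active and 217 vehicle; Week 4 success 37% and 22%; about 490 of 650 moderate; two-sided alpha 0.025; dataset counts 1, 3, 10; 25 PMM runs each.

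**Assumed, because the documents are silent.** Gap rate, between-visit correlation (0.3 to 0.7), Week 1 and 2 response, and gaps occurring at random.

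**1. The plan's own figure.** The plan gives none for imputation bias. Its power statement checks the inputs. Pooled rate = (433 x 0.37 + 217 x 0.22)/650 = 0.320. SE under the null = sqrt(0.320 x 0.680 x (1/433 + 1/217)) = 0.0388; under the alternative, sqrt(0.37 x 0.63/433 + 0.22 x 0.78/217) = 0.0365. Then (0.15 - 2.241 x 0.0388)/0.0365 = 1.73, so power is 95.8% (stated: more than 90%). For the moderate subgroup (327 and 163) it is 88.2% (stated: more than 80%).

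**2. Gaps allowed in the one-dataset band.** With three post-baseline visits, 650 x 3 = 1,950 and 2% is 39. If baseline counts as an expected visit, 650 x 4 = 2,600 and 2% is 52. The SAP does not say which. All 39 at one visit would be 39/650 = 6% of subjects.

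**3. Share of step 1 variance counted.** With M step 1 datasets, pooling counts (1 + 1/(25M)) x 25(M-1)/(25M-1) times the step 1 between-imputation variance. It should count 1 + 1/M.

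| M | Counted | Needed | Share |
|---|---|---|---|
| 1 | 0 | 2 | 0% |
| 3 | 0.685 | 1.333 | 51% |
| 10 | 0.907 | 1.100 | 82% |

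**4. Rough bound on dilution.** If step 1 lost the whole arm difference, the bias would be the filled fraction times the true difference. For an assumed early effect at Week 2 (29% and 14%), that is 0.06 x 15 = 0.90 points. At Week 1 (20% and 8%) it is 0.06 x 12 = 0.72 points. The other visits carry part of the difference, so simulated values should be smaller.

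**5. Simulated bias** (percentage points, against complete data in the same trials; both Week 1 and 2 endpoints). Rows 1 to 3 use assumed success at Weeks 1/2/4 of 8/14/22% on vehicle and, on active, 20/29/37% (early), 12/23/37% (gradual) or 8/16.5/37% (late), with correlation 0.4 or 0.7. The other rows come from a separate simulation.

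| Case | As planned | With both changes |
|---|---|---|
| 10 gaps at one visit, M = 1 | -0.12 to +0.07 | not reported |
| 20 gaps at one visit, M = 1 | -0.23 to +0.11 | -0.04 to 0.00 |
| 39 gaps at one visit, M = 1 | -0.49 to +0.23 | -0.10 to +0.04 |
| 2% over both visits, M = 1, correlation 0.6 | -0.08 to -0.06 | -0.01 to 0.00 |
| 5% over both visits, M = 3, correlation 0.6 | -0.20 to -0.12 | -0.04 to -0.01 |
| 5% over both visits, M = 3, correlation 0.3 | -0.43 to -0.26 | not run |
| Effect at Week 4 only, 2%, M = 1 | +0.02 to +0.15 | not run |
| Effect at Week 4 only, 5%, M = 3 | +0.05 to +0.36 | not run |

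In rows 1 to 3 the largest bias is 0.145 SE. In rows 4 to 6 the true differences are about 6 to 12 points. An extreme case, 97 gaps at one visit (5% of 1,950, or 15% of subjects) with M = 3 and early onset, gives up to about -1.0 to -1.3 points (about 0.35 to 0.4 SE); some runs gave as little as 0.2 SE.

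**6. Type I error at nominal 2.5%** (Monte Carlo error about 0.2 to 0.3 points).

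| Case | Complete data | As planned |
|---|---|---|
| Week 1 null, 20 or 39 gaps, M = 1 | 2.4-2.8% | 2.4-2.7% |
| No effect at any visit, 2%, M = 1 | 2.3-3.1% | 2.2-2.9% |
| No effect at any visit, 5%, M = 3 | 2.1-2.8% | 1.7-2.3% |
| Effect at Week 4 only, 2%, M = 1 | 2.6-2.7% | 2.6-2.7% |
| Effect at Week 4 only, 5%, M = 3 | 2.1-2.9% | 1.6-2.3% |

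In the first row's setting, the reported SE divided by the actual SD is 0.98-1.00 as planned, the same as with complete data. With both changes, type I error is 1.9-2.7% and the ratio 0.99-1.02. Imputing by arm with a single step 1 dataset gives 2.8-3.4% and 0.96-0.98.

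**The case against.** The strongest case against is that nothing is visibly harmed. Error rates and standard errors as planned match complete data when one dataset is used, and are slightly conservative with three. The usual bias is attenuation, which works against the sponsor. Both changes together move power by only about -0.5 to +1.5 points in the spread-gap runs.

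The SAP also limits the gaps. The windows in 5.4 are contiguous (Days 2-11, 12-22, 23-43) and admit unscheduled, retest and early termination values when the scheduled one is missing. Dropout is imputed in step 2, with treatment. Data removal after discontinuation for AE or lack of efficacy runs from the last-dose window onward, so it does not itself create intermittent gaps. The non-responder and observed-data analyses (12.2 and Table 5) do not use step 1. And the text does not forbid a by-treatment run; it simply does not state one.

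All of this stands, and it keeps the point minor. It does not make the stated method the better one. The acceptable calibration with one dataset arises because two departures offset each other: pooling the arms makes the estimate less variable, while the reuse of fills leaves variance uncounted. A programmer who sensibly added treatment but kept the one-dataset row would lose that balance.

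A reader might infer from the 0% share that the standard errors are too small and the error rate inflated. The simulations do not show this for the procedure as written. A reader might also infer that the primary result is at risk; step 1 does not fill Week 4.

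**Conclusion.** The point holds as a minor, cheap improvement. As written, step 1 can slightly bias the treatment difference in the last four alpha-controlled endpoints, in either direction depending on when the effect appears.

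The limit of roughly 0.15 SE applies only to up to 39 gaps at one visit with one step 1 dataset; it is not a general ceiling. The 97-gap case exceeds it, though the SAP's own expectation of few intermittent gaps makes that case unlikely. The absence of type I error inflation is likewise shown only for 1 and 3 datasets. The 10-dataset row and gaps that differ by arm were not simulated. The variance shares are algebra and need no assumed rate; every bias and error figure rests on the assumptions listed above.

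**What to change.** Make two changes to SAP 6.2.1 together:

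1. Run the step 1 MCMC separately by treatment group. The four-score normal model has 4 means and 10 variances and covariances, which 217 vehicle subjects can support.
2. Replace the 1/3/10 table with one step 1 dataset per final imputation, for example 100 step 1 datasets with one PMM draw each. The ordinary Rubin's rule then applies, and the question of what counts as an expected visit no longer matters.

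Do not adopt the first change with a single step 1 dataset. If a by-treatment run was already intended, state it and make the second change with it.

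Carry the same procedure through to the EASI and WI-NRS paragraphs of 6.2.1, to the tipping-point analysis in 6.2.3 (which reuses step 1), and to the dataset counts in 6.2.1 and 12.1.3.

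The cost is SAP wording, a small change to the imputation program and more computing time. Data collection is unchanged. In the simulations the two changes removed most of the bias but not all of it.
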